To minimize placebo or nocebo effects, devices (nVNS/sham) will have an identical appearance and all subjects will undergo identical training for self-administration. Both sham and nVNS treatments produce reliable sensations on the skin (sham device delivers a low dose DC voltage signal that results in paresthesia and prickling like sensations) and in preliminary surveys, subjects were unable to differentiate sham from active nVNS devices ($p>.1$). [name] will be unblinded to the treatment condition and provide the sham vs. nVNS device to the research team. Both the research team involved in data collection and subjects will be blinded (i.e., double-blind study design).

Neuroimaging: MRI scans take approximately 1 hour. The protocol includes one structural scan (structural T1) and up to four functional scans.

Anatomical Scan: During the anatomical scan, participants are asked to remain as still as they can for approximately 8 minutes. Pleasant pictures may be put up on a screen for participants to enjoy while the anatomical scan is occurring.

Heat pain task: The pain paradigm includes two conditions: “heat pain” (i.e., brief thermal heat temperature that produces heat pain sensations), or “warm stimulus” (i.e., brief thermal heat that produces warm sensations). Each temperature is delivered for 5 sec. Thermal stimuli, experienced as heat pain and warm, are delivered in a pseudo-random and counterbalanced order through a 9-cm² thermode (Medoc TSA-II, Ramat-Yishai, Israel) fastened to the subject’s left lower extremity (antero-medial ankle). Before scanning, subjects are pretested with several heat pain and warm thermal stimuli to ensure that temperatures are well tolerated. This setup is MRI safe and is currently used in [name] study and has been used in our prior fMRI studies.

Behavioral assessments: After enrollment participants will complete self-report measures in a designated, secure space located at VMRF or the UCSD Keck Center for fMRI. Data will be de-identified with a code and entered into a secure database on the VA server for future analysis. The code key will be kept separate from coded data and will not be available on the computers. No identifiable data will be stored with coded electronic research data. Assessment measures will be given at both baseline and follow-up visits. The research information that may be collected includes the following:

Questionnaires

Main outcome measures

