Inventory for Psychosocial Functioning (IPF). The IPF assesses functional limitations in interpersonal relationships, family, work, , parenting, education, and self-care) with good reliability and validity.

Screening questionnaires

Structured Clinical Interview for DSM-5 (SCID). This semi-structured interview will be used to establish a DSM-5 AUD diagnosis. Stem questions will be used to screen for inclusions/exclusions.

Alcohol withdrawal symptoms. The Clinical Institute Withdrawal Assessment of Alcohol Scale, Revised (CIWA-Ar) is a short form (5 min.) to assess physiological and psychological symptoms of alcohol withdrawal.

Timeline follow-back (TLFB). The TLFB is a standard tool used to document number and types of drinks consumed per day during a specified time frame. The TLFB will be used to measure alcohol use (percentage days abstinent, amount consumption, length of use episodes, and current alcohol use pattern) use during the 90 days preceding baseline interview, during, and between interviews.

Human Subjects

The participants in this study will be 20 physically healthy male Veterans with current AUD. Subjects will be recruited via flyers posted in VA mental health and primary care, from advertisements in print and web-based media, and from VA substance use and other psychiatry clinics. Participants will be asked to refrain from drinking alcohol 24 hours prior to each study visit and will be randomly assigned to receive nVNS or sham stimulation (10 nVNS/10 sham) prior to performing a well-validated fMRI task designed to assess the neural correlates of physical distress (pain processing via heat stimulus). Subjects will then be instructed to self-administer nVNS at home for 7 days and return for a follow-up visit (same protocol will be repeated at follow-up). Behavioral assessments of drinking-related consequences, functional disability and health, psychological and physiological distress, and craving will be administered at baseline, after stimulation, and at follow-up (post 7 days of nVNS/sham self-administration).

Inclusion Criteria.

1. Male subjects between 21 and 65 years, any race or ethnicity.
2. Meet current DSM-5 diagnosis of AUD (Structured Clinical Interview for DSM-5 (SCID) interview 1) with at least one functional disability due to alcohol use, current alcohol craving, and current heavy drinking (>4 drinks on any given day within the last week OR more than 14 drinks per week).

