Subjects with a score higher than 9 on the Clinical Institute Withdrawal Assessment for Alcohol Scale (CIWA-Ar) will be excluded from the study and immediately referred to the hospital as it may not be safe for these individuals to abstain from alcohol without medical supervision.

Data analysis

Image analysis pathway: Image processing will be done with the AFNI software package (afni_proc.py). Specifically, the EPI timeseries despiked (3dDespike), slice time corrected (3dTshift), and co-registered, which will provide motion parameters (x, y, z, roll, pitch, yaw) for each EPI image's registration to the optimal base image (align_epi_anat.py:3dvolreg). Based on the distribution of these average motion parameters, subjects will be excluded if the average in any one of these parameters exceeds 2 absolute deviations from the mean. All EPI timeseries will be moved to MNI coordinates (align_epi_anat.py: 3dQWarp), blurred to 2x voxel width (to account for individual variations in the anatomical landmarks (3dBlurToFWHM), and converted to percent signal change (3dcalc). Preprocessed time series data for each individual will be analyzed using a multiple regression model. A multivariate regressor approach will be used to relate changes in EPI intensity to differences in task characteristics. Regressors of interest include: 1) Pain [i.e., what activates during pain stimuli], 2) Non-pain [i.e., what activates during non-painful stimuli], 3) Pain anticipation [i.e., what activates during anticipation of pain stimuli] and 4) Non-Pain anticipation [i.e., what activates during anticipation of non-painful stimuli]. To reduce the false positives induced by auto correlations of the time series, data will be fit using the AFNI program 3dREML. Statistical analysis of fMRI derived data will be obtained with standard statistical techniques.

Group analyses. Statistical analyses will be performed to evaluate treatment acceptability, if nVNS improves functional outcomes, quality of life, emotional and physical

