To test hypothesis 3: We will use linear mixed effects models to assess the impact of treatment group (nVNS/sham) by time (baseline/7 days FU) in a 2-way interaction on insular activation. Exploratory voxel-wise analyses will also be performed to examine effects of group on amygdala, anterior cingulate, and striatum. The MNI transformed percent signal change from the functional data will be contrasted in a voxel-based linear mixed effects model (AFNI 3dLME), with group and time factors entered as primary contrasts. In addition, subject will be entered as a random factor. A threshold adjustment method based on Monte-Carlo simulations will be used to guard against identifying false positive areas of activation. These simulations will use a 2-parameter model fit calculated in the 3dFWHMx (ACF) function using a measured blur and requiring a voxel-based threshold at $.001$ and cluster level thresholding at $.01$ or with 22 for group and time effects for the whole brain analysis.

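### The motion exclusion rule averages head position relative to a base image, so as written it can miss brief or back-and-forth movement and can flag a head that was otherwise still (exploratory Aim 3 only)

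*Combined protocol and SAP*

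**What the plan says.** Under Data analysis, Image analysis pathway, registration yields "motion parameters (x, y, z, roll, pitch, yaw) for each EPI image's registration to the optimal base image". The next sentence sets the rule, which works from how the per-subject averages are spread: "subjects will be excluded if the average in any one of these parameters exceeds 2 absolute deviations from the mean".

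The word absolute describes the deviation used as cut-off, not the parameter being averaged. The text does not say whether values are averaged with their sign, as absolute values, or as differences between successive images. It does not say whether the base image comes from the same run. The Neuroimaging paragraph states: "The protocol includes one structural scan (structural T1) and up to four functional scans".

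The pathway also lists despiking and volume registration. It states no other motion exclusion and no censoring of volumes. The scans that pass feed the Aim 3 models, which "assess the impact of treatment group (nVNS/sham) by time (baseline/7 days FU) in a 2-way interaction on insular activation", and the exploratory voxel-wise analyses. The Human Subjects section plans 20 subjects, 10 per arm.

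**The concern.** Registration parameters are shifts and rotations away from a reference position, and they carry a sign. Their average over a run says where the head lay on average. Movement out and back contributes little to it, and symmetric movement contributes nothing. A single early shift or a constant offset contributes a lot.

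The task makes this more than a formality. Heat stimuli last 5 seconds, and a flinch followed by a return is an obvious kind of movement in a pain paradigm. Such movement would tend to coincide with the pain regressor, so it is the kind that screening most needs to catch. If it passes, it can add noise or false activation to the insular and voxel-wise results. If a usable scan is dropped instead, the loss comes out of at most 10 subjects per arm.

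The choice of cut-off is a separate matter: any threshold on the same signed average would still pass a head that oscillates symmetrically.

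**Working it through.** The plan gives no performance figure for this rule, so there is nothing to reproduce.

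**Inputs from the documents:** six parameters per image relative to a base; an average per parameter; exclusion beyond 2 absolute deviations on any one; 20 subjects. **Assumed:** 300 images per run, and every movement pattern below.

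**Step 1. What each summary measures.** Let p(t) be one parameter at image t, with T = 300.

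- Signed mean A = Σp(t) / T
- Absolute mean B = Σ|p(t)| / T
- Mean step S = Σ|p(t) − p(t−1)| / (T − 1)

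| Pattern | A (mm) | B (mm) | S (mm per image) |
|---|---|---|---|
| Alternates +1/−1 mm every image | (150 − 150)/300 = 0 | 300/300 = 1 | 598/299 = 2.0 |
| 20 flinches of 1 mm, 2 images each | 40/300 = 0.13 | 0.13 | 40/299 = 0.13 |
| One 1 mm shift at mid-run, otherwise still | 150/300 = 0.5 | 0.5 | 1/299 = 0.003 |
| Still, 0.5 mm from the base | 0.5 | 0.5 | 0 |
| Steady drift from 0 to 3 mm | 1.5 | 1.5 | 3/299 = 0.010 |

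The flinching head moves 40 times as much per image as the head that shifts once (40/299 against 1/299). Its average is nevertheless 3.75 times smaller (0.5/0.133). Averaging absolute values leaves that ranking unchanged. Drift does raise the average, so the rule responds to some kinds of movement.

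**Step 2. How often it matters.** Simulation with 20 subjects, six parameters and 500 replicates. Movement is autoregressive (lag-one correlation 0.9), with log-normal amplitude across subjects (log-mean −1.2, log-SD 0.7). The rule is the signed mean, 2 mean absolute deviations, either side, any parameter. The worst mover is the subject with the largest mean image-to-image change. A base from another run adds a constant offset of SD 0.5, unrelated to movement.

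| Base image | Drift | Worst mover kept | Stillest excluded | All excluded |
|---|---|---|---|---|
| Same run, near median position | no | 0.6% | 0% | 38.5% |
| Same run, near median position | yes | 0.4% | 0% | 39.1% |
| Same run, random image | no | 1.6% | 0.2% | 38.5% |
| Same run, random image | yes | 0.8% | 0.2% | 38.9% |
| Another run | no | 37.8% | 47.2% | 48.3% |
| Another run | yes | 6.8% | 22.8% | 43.6% |

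**Step 3. Sensitivity to the offset.** A second model uses uncorrelated jitter (median 0.22 mm, log-SD 0.7) plus a slow offset, with 20 subjects and 2,000 runs. Jitter of 0.22 mm averages down to 0.22/√300 = 0.013 mm, so the offset decides who is excluded.

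- Offset independent of jitter (SD 0.1-0.3 mm): the worst four movers excluded 50-55% of the time, against 49% for all subjects.
- Offset proportional to jitter: worst four 92%, stillest four 1%.
- Offset proportional to the square root of jitter: worst four 83-84%, stillest four 9-10%.

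**Step 4. A movement measure instead.** In the Step 2 model, mean absolute image-to-image change with an upper-side cut-off of 2 mean absolute deviations flagged the worst mover in 99-100% of replicates, the stillest in 0%, and about 10% of subjects overall. Part of this is built in, because the worst mover was defined by image-to-image change. It was also run per parameter, not on a single combined figure.

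**The case against.** **The text never says the average is signed.** This is correct. If absolute values are intended, symmetric oscillation no longer cancels (B = 1 mm in the first pattern). The flinch-against-shift ranking does not improve, however. In the Step 2 model with a base from another run, an upper-side rule on the absolute mean still kept the worst mover in 13.4% of replicates without drift and 6.6% with it (excluded in 86.6% and 93.4%). It excluded the stillest in 23.4% and 10.4%. The same change of wording settles both readings.

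**A reader might infer that the rule keeps the worst movers and discards still heads.** The documents do not support that as a general statement. With a same-run base the simulated rule nearly always caught the worst mover and almost never excluded the stillest. Even with a base from another run, the worst mover was excluded more often than the stillest (62% against 47% without drift, 93% against 23% with it).

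**A reader might also infer that exclusions would be nearly unrelated to scan quality.** That follows only if the offset is independent of movement (Step 3), and the documents contain no motion data to support it.

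**The illustrations are extreme.** A head alternating by exactly 1 mm on every image is unrealistic, and a 1 mm shift is real movement. Both points are fair. The flinch pattern is less artificial, but it too is assumed.

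**Other safeguards exist.** Despiking and registration are stated, and they reduce motion effects without removing them. The plan lists only its regressors of interest, so motion regressors are not ruled out. They are simply not stated.

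**The high overall exclusion rates come from the cut-off.** This stands. The 38-48% rates in Step 2 largely reflect 2 absolute deviations applied to any of six parameters, and they are not evidence for the present point.

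**Conclusion.** The concern holds as a weakness in the stated metric. Taken literally, the rule measures average displacement from a base image. It can under-count oscillation and brief flinch-and-return movement, and it can flag a head that shifted once or lay off the base.

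The size is conditional. Under the assumed motion models, the chance of keeping the worst mover runs from 0-2% (same-run base) to 7-38% (base from another run). The chance of excluding the stillest subject runs from 0-0.2% to 23-47%. Which range applies cannot be settled from the documents, because neither the source of the base image nor the pattern of movement is given.

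The consequence is confined to Aim 3, which the plan labels exploratory. The feasibility and acceptability results (Aim 1) and the questionnaire outcomes (Aim 2) are untouched. The change is worth making because the repair is cheap and does not depend on how the ambiguity is resolved.

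**What to change.** In the exclusion sentence of the Image analysis pathway, replace the average of any single parameter with each scan's mean volume-to-volume displacement. This is the Euclidean norm of the differences in the six parameters between successive images, averaged over the task runs at each visit. Exclude only when that single figure is too high. State how rotations are converted to the scale of translations, and whether a high value removes that visit's scan or the subject, since the present wording removes subjects.

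The cost is one sentence, and the figure comes from parameters the pipeline already produces. The minor downside is that a scaling convention for rotations must be chosen. The change does not define the absolute deviation used as the cut-off, which needs its own clarification.

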distress, and alcohol craving in Veterans with AUD, and if nVNS alters neural activation patterns in brain regions involved in perception and awareness of distress. The family-wise error (FWE) rate will be set at $p=.05$ as we have limited power to more stringently correct for multiple comparisons. We will examine correlations between dependent variables and potentially confounding factors, such as age, AUD severity, or level of depression and anxiety, and covary for these factors if necessary. In addition, we will covary for TLFB data (i.e., days since last drink, number of drinks, percent days drinking, etc.).

Aim 1: The primary aim is to establish feasibility and acceptability of using nVNS as a rehabilitative treatment for AUD in Veterans within the VA San Diego Healthcare System (VASDHS).

To test hypothesis 1: Recruiting 16 subjects within 12 months as well as treatment adherence and retention rates of $>75\%$ will be considered feasible. A mean group score for treatment acceptability (TAQ) will be calculated for the nVNS group and a value of ≥ 5 will be considered an acceptable treatment (17).

Aim 2 (exploratory): The secondary aim is to evaluate preliminary effectiveness of nVNS in improving functional outcomes and quality of life, as well as in reducing distress and alcohol craving.

To test hypothesis 2a: We will use linear mixed effects (LME) models to assess the impact of treatment group on Substance Use Recovery Evaluator (SURE) and WHOQOL-BREF scores. Specifically, we will test group (nVNS/sham) by time (baseline/7 days FU) interactions.

To test hypothesis 2b: We will use LME models to assess the impact of treatment group on Beck Anxiety Inventory and PROMIS Pain Interference Scale scores. Specifically, we will test group (nVNS/sham) by time (baseline/7 days FU) interactions.

To test hypothesis 2c: We will use LME models to assess the impact of treatment group on Alcohol Urge Questionnaire scores. Specifically, we will test group (nVNS/sham) by time (baseline/7 days FU) interactions.

Aim 3 (exploratory): The final aim is to alter neural activation patterns in brain regions subserving perception and awareness of emotional and physical distress using nVNS.

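### The plan states a family-wise error rate of .05 for the group analyses, but nothing in it holds that rate across the five Aim 2 tests

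*Combined protocol and SAP*

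**What the plan says.** The opening of Group analyses (Data analysis) announces tests of treatment acceptability, functional outcomes, quality of life, distress and craving, and of "if nVNS alters neural activation patterns in brain regions involved in perception and awareness of distress". The next sentence is: "The family-wise error (FWE) rate will be set at $p=.05$ as we have limited power to more stringently correct for multiple comparisons". Read in order, the error rate applies to the clinical and the neural outcomes.

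The tests are then listed by hypothesis, each as a group (nVNS/sham) by time (baseline/7 days) interaction in a linear mixed model:

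- 2a: "assess the impact of treatment group on Substance Use Recovery Evaluator (SURE) and WHOQOL-BREF scores" (two tests).
- 2b: "assess the impact of treatment group on Beck Anxiety Inventory and PROMIS Pain Interference Scale scores" (two tests).
- 2c: "assess the impact of treatment group on Alcohol Urge Questionnaire scores" (one test).
- 3: group "by time (baseline/7 days FU) in a 2-way interaction on insular activation" (one test), with exploratory voxel-wise analyses named separately.

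The section labels both of these aims exploratory; for Aim 2 it reads "Aim 2 (exploratory): The secondary aim is to evaluate preliminary effectiveness of nVNS". Aim 1 has no alpha-level test. It is judged on "Recruiting 16 subjects within 12 months as well as treatment adherence and retention rates of" more than 75%, and on a mean TAQ score of at least 5 in the nVNS group.

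The one multiplicity procedure is at the end of hypothesis 3: a Monte-Carlo threshold adjustment based on measured image blur, with a voxel threshold of .001 and a cluster level of .01. The clause giving the cluster level is garbled in the text available, and refers to the whole-brain analysis.

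**The concern.** A family-wise error rate belongs to a defined set of tests together with a procedure. The plan gives a value and supplies neither for the Aim 2 outcomes: no family, per-test alpha, adjustment, testing order or lead outcome. The cluster threshold cannot fill the gap, because it works on maps of activation and not on questionnaire scores.

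The sentence also pulls in two directions. It names a family-wise rate, yet gives limited power as the reason for not correcting further. That reads more like .05 for each test.

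What is at stake is reporting. One interaction with p<.05 among five scales could be published under a 5% family-wise claim that no written method supports. No success rule depends on these p-values.

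**Working it through.** **Inputs from the plan.** Family-wise level .05, sidedness not stated. Five Aim 2 tests (2 + 2 + 1) and one insula test. Allocation 10 nVNS/10 sham (Human Subjects).

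**Assumptions, because the plan gives no figure.** Two-sided .05 for each test, one score per scale, no covariates, and a common correlation ρ among the test statistics, varied from 0 to 0.9.

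**Can the plan's .05 be reproduced?** It is a chosen target, with no per-test level or procedure from which to derive it. With each test at .05, the family-wise rate equals .05 only for a single test: 1 − 0.95¹ = .05.

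**Independent tests:** 1 − 0.95^k.

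- k = 2: 1 − 0.9025 = .0975
- k = 5: 1 − 0.7738 = .2262
- k = 6: 1 − 0.7351 = .2649

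**Equally correlated tests.** With c = 1.96 and a shared standard normal component u, the rate is

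1 − ∫ φ(u) [Φ((c − √ρ·u)/√(1−ρ)) − Φ((−c − √ρ·u)/√(1−ρ))]^k du.

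| Family | ρ = 0 | ρ = 0.5 | ρ = 0.8 | ρ = 0.9 |
|---|---|---|---|---|
| 2 tests (2a or 2b alone) | 9.75% | 9.1% | 7.8% | 7.0% |
| 5 tests (Aim 2) | 22.6% | 18.3% | 12.7% | 10.2% |
| 6 tests (Aim 2 + insula) | 26.5% | 20.7% | 13.9% | 10.8% |

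If each hypothesis were its own family, 2c and the insula test would each be a single test at 5%. If the insula test is independent of the five scales, the six-test rate is 1 − (1 − .1828)(.95) = 22.4% at ρ = 0.5 among the scales, and 1 − (1 − .1016)(.95) = 14.7% at ρ = 0.9.

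Simulated t tests on change scores with 10 per arm gave .227, .185 and .101 for five tests at ρ = 0, 0.5 and 0.9, so the small sample does not alter the picture.

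**The count is a minimum.** WHOQOL-BREF has four domains, and the plan does not say whether a total or the domains are tested. With four domain tests in place of one, the count is 6 − 1 + 4 = 9, and the independent rate is 1 − 0.95⁹ = 36.98%.

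**Cost of real control.** Holm's first step uses .05/5 = .01 or .05/6 = .00833. For an unadjusted comparison of change scores (noncentral t, 80% power):

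| Per arm | α = .05 | α = .01 | α = .00833 |
|---|---|---|---|
| 10 | 1.325 SD | 1.686 SD | 1.726 SD |
| 8 | 1.507 SD | 1.943 SD | 1.992 SD |

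At 10 per arm, power for a 1.325 SD difference falls from 80% to 54.5% (α = .01) or 51.6% (α = .00833). Eight per arm assumes that the 16 recruits of the feasibility criterion split evenly and all complete.

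**The case against.** **The aims are exploratory, so family-wise control is optional.** This stands, and it limits the weight of the point. It does not make the sentence accurate: an optional control that is claimed still needs a method. The sentence does admit limited power, which lessens the risk of misleading a reader but does not tell that reader which rate applies.

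**A missing procedure does not show that the tests will go unadjusted.** This also stands. The sponsor could apply Holm and satisfy the sentence as written. The error rates above are conditional on .05 per test.

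**The layout suggests one family per hypothesis.** That is possible, and it gives the smallest figures. The two-test families (2a and 2b) still exceed .05 at every correlation examined, so the objection reduces the size without removing the defect.

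**The imaging correction is the procedure meant.** A reader might infer the opposite, that the .01 cluster level proves the .05 sentence excludes the image analyses. The documents do not support that inference. The .01 sits in a garbled clause tied to the whole-brain analysis, no level is given for the insula or the other named regions, and a .01 cluster level would also satisfy a .05 ceiling. So the .05 may have been meant for image data, and the status of the insula test is open. None of this brings the five questionnaire tests under any procedure.

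**Conclusion.** The point holds for the five Aim 2 tests: a family-wise rate of .05 is stated and nothing in the plan delivers it. That follows from the text and needs no assumption. For the insula test the plan is unclear, not demonstrably uncontrolled.

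The size is conditional on two-sided .05 per test and on assumed correlations. It runs from 7.0% (one two-test hypothesis, ρ = 0.9) through 10.2% to 22.6% (five tests) up to 26.5% (six independent tests), against the stated 5%. If the insula test falls under the cluster-corrected map, the five-test figures apply.

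A reader might infer that the trial has a false-positive rate of about a quarter, or that the plan has no multiplicity control at all. Neither is supported: no per-test level is written, and the voxel-wise maps do have a correction. Nor is the trial's main conclusion at risk, since Aim 1 rests on descriptive thresholds.

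Severity is minor to moderate.

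**What to change.** Replace the family-wise sentence. The sponsor should state which of two meanings is intended.

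- **(a) No family-wise control.** State that each Aim 2 group-by-time test uses a per-comparison two-sided alpha of .05 without control of the family-wise rate, that the p-values are exploratory, and that estimates are reported with 95% CIs. State also whether the insula test is treated the same way or falls under the cluster-corrected map. Keep the voxel-wise correction.
- **(b) Family-wise control at .05.** Name the family (the five Aim 2 tests, or six with the insula) and specify Holm.

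Under either option, say whether WHOQOL-BREF enters as one score or as four domains, since that sets the count, and restate the cluster-level clause legibly with the analyses it covers.

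Option (a) changes no test, estimate or sample size; its downside is that the stated error control becomes less favourable. Option (b) costs power: at 10 per arm, the difference detectable with 80% power at Holm's first step rises from about 1.33 SD to 1.69 SD (five tests) or 1.73 SD (six).

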Subjects will be asked to come in for a total of two study visits (baseline and follow-up) and self-administer nVNS/sham twice a day for a period of 7 days in between these visits. During both visits, subjects will be asked to complete behavioral assessments and to participate in an fMRI scan. If subjects are unable to come in for their follow-up person, they will be given the option to complete the questionnaires remotely (via telehealth, phone, or mail). Procedures for this are detailed under "Covid-19 adaptations". Please see figure below for a schematic and chronological presentation of the research components. Subjects will be randomly assigned to receive nVNS or sham stimulation prior to performing a well-validated fMRI task designed to assess the neural correlates of

physical distress (pain processing via heat stimulus). During each scan (baseline and follow-up), nVNS or sham stimulation will be administered once for 120 seconds. Subjects will remain in the same condition (sham/nVNS) assigned at baseline and be instructed to self-administer nVNS/sham at home for 7 days and return for a follow-up visit (treatment adherence and adverse events will be measured with a daily log and interview). Behavioral assessments of functional disability, quality of life, psychological and physical distress and craving will be administered at baseline, after stimulation, and at follow-up (post 7 days of nVNS/sham self-administration). After completion of the study visit, subjects will be evaluated for any side effects from stimulation and sent home. The patient will be instructed to carry out stimulation (sham or nVNS) twice a day for the following 7 days. Subjects will be instructed to drink "as usual" during the 7-day treatment window, with the intention to observe whether nVNS leads to reduced alcohol use, and will be asked to abstain again for 24 hours prior to their follow-up study visit on day 9 (allowing subjects to administer nVNS/sham on day 8 ad lib). Drinking behavior during the trial (as well as at baseline and follow-up) will be quantified with the Timeline Follow Back. Treatment acceptability will be assessed at follow up. We previously established feasibility of applying nVNS/sham in healthy individuals (Lerman et al., 2019) and have completed similar work with Veterans. However, this work has not been done in heavy drinkers.

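### The only test named for the insula is group by time, which cannot see an nVNS effect of equal size at both visits, because both heat-pain scans appear to follow stimulation

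*Combined protocol and SAP*

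**What the plan says.** Data analysis, Aim 3 (hypothesis 3), gives the insula one test, a linear mixed model for "treatment group (nVNS/sham) by time (baseline/7 days FU) in a 2-way interaction on insular activation". It then adds: "Exploratory voxel-wise analyses will also be performed to examine effects of group on amygdala, anterior cingulate, and striatum". The voxel-wise 3dLME is specified "with group and time factors entered as primary contrasts", and the cluster thresholds are given for "group and time effects for the whole brain analysis". The question set in Group analyses is broader: "if nVNS alters neural activation patterns in brain regions involved in perception and awareness of distress".

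On timing, Design and Methods (Approach) states: "During each scan (baseline and follow-up), nVNS or sham stimulation will be administered once for 120 seconds". It also states: "Subjects will be randomly assigned to receive nVNS or sham stimulation prior to performing a well-validated fMRI task". The Study outline lists stimulation ahead of the anatomical and heat-pain scans at both visits. Human Subjects says that follow-up repeats the baseline procedure. Participants keep the same arm throughout. No heat-pain run before stimulation is described.

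**The concern.** A group-by-time interaction measures a treatment effect when the first time point is untreated. Here the first scan appears to be taken after the first dose of nVNS or sham, so any acute effect is already in the baseline value and is subtracted out.

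The interaction remains valid for what the week of home use adds. It does not by itself answer whether nVNS alters insular activation. A real effect present at both visits would give a null result that could be read as no insular effect. An effect that fades would give a negative interaction, and without the per-visit differences the reader could not tell that nVNS had differed from sham at visit 1.

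The same interaction suits Aim 2 better, because the behavioural measures "will be administered at baseline, after stimulation, and at follow-up", which gives them a baseline separate from the post-stimulation point. No such point is described for the scan.

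**Working it through.** The plan gives no effect size, SD, correlation or power for Aim 3, so there is no stated figure to reproduce.

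**Inputs from the documents.** Ten per arm (Human Subjects); 16 in total as the recruitment criterion, taken here as 8 per arm (Aim 1, hypothesis 1); alpha .05 (Group analyses; two-sided assumed).

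**Assumptions.** SD of 1 at each scan, between-visit correlation ρ of .3, .5 or .7, and the effect sizes below. Covariates, motion exclusions and dropout are ignored.

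**Contrasts.** Let d1 and d2 be the nVNS-minus-sham insular differences at visit 1 (acute) and follow-up (acute plus 7-day).

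- Group by time estimates d2 − d1, with per-subject variance 2(1 − ρ).
- A one-visit contrast estimates d1 or d2, with variance 1.
- The two-visit group effect estimates (d1 + d2)/2, with variance (1 + ρ)/2.

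If d1 = d2, the interaction is zero whatever the size of the effect. If d1 = 1.0 and d2 = 0.5, it is −0.5, opposite in sign to the effect at both visits. This part is algebra and needs no assumed effect size.

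**Power.** Two-sample t with 18 df and noncentrality = contrast / √(variance × 2/10). For example, 1.0 SD at one visit gives 1/√0.2 = 2.24 and power .562. Where three figures are shown they are for ρ = .3/.5/.7.

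| True effect (SD) | Group by time | One-visit contrast | Two-visit group effect |
|---|---|---|---|
| d1 = d2 = 1.0 | 5/5/5% | 56% | 75/69/63% |
| d1 = d2 = 0.5 | 5/5/5% | 19% | 26/23/21% |
| d1 = 0, d2 = 1.0 | 43/56/78% | 56% (follow-up) | 26/23/21% |
| d1 = 1.0, d2 = 0 | 43/56/78%, negative direction | 56% (visit 1) | 26/23/21% |

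A simulation at ρ = .5 with d1 = d2 = 1.0 agrees: mean interaction 0.00 with rejection rate .049, and two-visit group effect .685. No single contrast serves every case. The two-visit effect is best for a stable effect and worst for one confined to a single visit.

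**Precision of a per-visit estimate.** The 95% half-width is t × √(2/n). At 10 per arm it is 2.101 × √0.2 = 0.94 SD; at 8 per arm it is 2.145 × √0.25 = 1.07 SD.

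**Multiplicity if p values were claimed.** In 200,000 simulated null trials, testing visit 1, follow-up and the interaction each at .05 gave at least one false positive in 12.4/12.5/12.3%. Holm lowers this to 4.4/4.5/4.4%. It also cuts the interaction's power for a purely 7-day effect of 1.0 SD from 43/56/78% to 29/40/63%, and a per-visit contrast for a stable 1.0 SD effect from 56% to 40%.

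**The case against.** There are five points on the other side.

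- **The run order is not certain.** The visit schematic was not available to this review. The text also says stimulation is given during the scan, and Neuroimaging allows as many as four functional scans although only one task is described. A pre-stimulation run is possible. This stands as a limit on confidence. Still, no such run is described and the time factor has only two levels, so the reading taken here is the more natural one.
- **A group effect is already planned.** The 3dLME group contrast covers insular voxels. This stands in part. That test uses a .001 voxel threshold with cluster correction, the regions singled out for a group effect do not include the insula, and its power cannot be computed from the documents.
- **The interaction is a legitimate target** for a trial of a week of home use. It is, but the plan does not limit its question to that.
- **The stakes are modest.** Aim 3 is exploratory, the primary feasibility and acceptability aim is untouched, and nothing in the plan says a null interaction would be reported as no effect. All of this stands.
- **The remedy yields little.** Per-visit intervals are wide, and no two-visit insular contrast is added although it is the strongest for a stable effect. The width is real. The two per-visit estimates cover both the stable and the 7-day case, and the planned voxel-wise group effect stays in place.

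**Conclusion.** The concern holds on the visit order as described. The one test named for the insula estimates d2 − d1 and has only its 5% false-positive rate when the effect is equal at both visits. In that case, with an assumed 1.0 SD effect and 10 per arm, a single-visit contrast would detect it in 56% of trials and the two-visit effect in 63–75%. The zero expectation is exact; the power figures depend on the assumed effect and correlation. If a pre-stimulation heat-pain run is acquired and used as the baseline, the problem disappears. The mismatch is confined to an exploratory aim but is cheap to correct, so it should be corrected.

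**What to change.** In the hypothesis 3 text:

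1. Keep group by time as the named insular test at .05, and label it as the change in the nVNS effect after 7 days of home use.
2. From the same model, report the insular nVNS-minus-sham difference at visit 1 (acute) and at follow-up (acute plus 7-day) as exploratory estimates with 95% CIs, without p-value claims.
3. State that a null interaction is not evidence of no insular effect.
4. Enter group, time and group by time in 3dLME, so that the region-of-interest and voxel-wise analyses report matching contrasts. Keep the planned group effect.
5. State the order of runs within each scan. If a pre-stimulation run is acquired, say so and use it as the baseline.

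The cost is SAP wording. The scans and the model are already planned, and the interaction keeps its alpha and power. The downside is two more exploratory estimates, each imprecise. Holm is deliberately not used, because no p values are claimed for the added estimates and it would weaken the planned interaction.
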